- Gag reflex or any contraindication to X-ray
- Refusal to participate

5. Interventions

Each participant received:

- Four horizontal bitewing radiographs (control)
- Four vertical bitewing radiographs (experimental)
- Radiographs were taken using a standardized film holder and a 3-mm orthodontic wire attached to the sensor for magnification calibration.

Observers included two restorative specialists (for caries) and two periodontists (for bone loss), all blinded to group assignments.

6. Measurements

- Caries Assessment:

Evaluated using a 5-point diagnostic confidence scale and a secondary clarity scale.

- Bone Loss & Furcation:

Measured from the CEJ to the alveolar crest using calibrated software. Furcation involvement was assessed using a 5-point scale.

- Intra- and Inter-Observer Agreement:

Evaluated with Kappa statistics and intra-class correlation coefficients.

7. Sample Size Calculation

- **Software:** G*Power 3.1.9

- Effect size: 2.1 mean difference

- SD: 5.2

- Power: 80%

- Alpha: 0.05

- Required Sample: 20 patients

8. Statistical Analysis

Statistical Analysis

Software:

Data will be analyzed using IBM SPSS Statistics version 23.0 (IBM Corp., Armonk, NY, USA) and ROC analysis will be performed using MedCalc or equivalent software for diagnostic

accuracy assessment.

8.1 Analysis Population:

All radiographs captured for the 20 enrolled participants (160 total bitewing images: 80 vertical, 80 horizontal) will be included. Both intention-to-treat and per-protocol analyses will be conducted. All images were anonymized, and evaluators were blinded to image type and patient identity.

8.2 Primary Analysis:

Primary Endpoints:

- Detection of approximal caries (presence and clarity)
- Alveolar bone level measurements (in mm)
- Presence and clarity of furcation involvement

Tests for Diagnostic Accuracy:

- **Receiver Operating Characteristic (ROC) Analysis:**

ROC curves were plotted for each evaluator for both vertical and horizontal bitewings.

The Area Under the Curve (AUC) was computed to assess diagnostic accuracy compared to the “gold standard” (combined clinical and radiographic diagnosis).

- AUC values close to 1.0 indicate higher accuracy.
- Comparisons of AUCs between vertical and horizontal bitewings were conducted using DeLong’s test.
- **Sensitivity and Specificity:** These were calculated for each radiographic method in detecting caries and furcation involvement. 95% confidence intervals were provided.

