8.3 Observer Reliability:

- **Intra-Observer Agreement:** Measured using **Weighted Kappa coefficients** for repeated readings of the same radiographs by the same observer at two time points.

- **Inter-Observer Agreement:** Measured using **Intraclass Correlation Coefficient (ICC)** for bone level measurements and **Weighted Kappa** for caries and furcation rating scores between observers.

Interpretation of Kappa values:

- < 0.20: Poor
- 0.21–0.40: Fair
- 0.41–0.60: Moderate
- 0.61–0.80: Substantial
- 0.81–1.00: Almost perfect

8.4 Comparative Tests Between Vertical and Horizontal Bitewings:

- **Wilcoxon Signed-Rank Test:** Used to compare the mean alveolar bone loss measurements (mesial, distal, and total) between vertical and horizontal bitewings (non-parametric paired comparison).
- **McNemar Test:** Applied to assess paired binary outcomes (e.g., presence vs. absence of caries or furcation involvement) between imaging modalities.
- **Chi-Square Test:** Used to compare proportions of overlapping contacts and furcation detection in both modalities.
- **Descriptive Statistics:**
 - Mean \pm standard deviation (SD) for continuous variables (e.g., bone level)
 - Frequencies and percentages for categorical variables (e.g., tooth type, gender distribution)

8.5 Handling of Missing Data:

- Missing image evaluations (if any) were addressed via sensitivity analysis using pairwise deletion, given the minimal expected rate due to controlled data acquisition and blinded

scoring.

8.6 Effect Size Reporting:

- For Wilcoxon and McNemar tests, effect sizes (r) were reported.
- For ROC analysis, 95% CI of AUCs and comparison P-values were provided.

9. Expected Outcomes

- Vertical bitewings will show higher sensitivity in detecting furcation involvement.
- Vertical bitewings will provide better diagnostic accuracy for approximal caries and alveolar bone loss.
- Vertical bitewings will have superior intra- and inter-observer reliability in detecting pathology.

10. Ethical Considerations

- All participants provided informed written consent.
- Ethical approval was secured from local ethics board.
- All data were anonymized and securely stored.
- Participants had the right to withdraw at any time without consequences.

11. Timeline

Phase	Duration
Ethical Approval	Completed
Participant Recruitment	2 months
Radiograph Collection	2 months
Data Analysis	1 month

Phase	Duration
Manuscript	1 month

12. Dissemination Plan

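### Section 8.2 builds ROC curves reader by reader but never says how two readers' AUC comparisons become one answer about vertical versus horizontal bitewings

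*Combined protocol and SAP*

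**What the plan says.** The primary objective in Section 2 concerns the modality: whether vertical or horizontal bitewings are more accurate. The readers are set out in Section 5: "Observers included two restorative specialists (for caries) and two periodontists (for bone loss), all blinded to group assignments". No furcation reader is named.

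Under the ROC heading of Section 8.2, "ROC curves were plotted for each evaluator for both vertical and horizontal bitewings", and then "Comparisons of AUCs between vertical and horizontal bitewings were conducted using DeLong’s test". The second sentence does not mention the evaluator. Section 8.6 adds "For ROC analysis, 95% CI of AUCs and comparison P-values were provided".

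Sensitivity and specificity are described by method: "These were calculated for each radiographic method in detecting caries and furcation involvement". How two readers feed one such estimate is not stated. Section 8.3 uses weighted kappa "for caries and furcation rating scores between observers" and an ICC for bone level. These measure agreement and do not combine accuracy.

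The document contains no reader-averaged AUC, multi-reader model, consensus reading, lead reader or rule for discordant readers.

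**The concern.** The question is about the modality, but the ROC output is per reader. For caries, where two restorative specialists rate the images, the plan most naturally yields two AUC differences, two confidence intervals and two p-values. If one reader's comparison is significant and the other's is not, the plan gives no conclusion, and the choice of which result to emphasise is left until after the results are seen.

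There is also a possible loss of precision. Two readings of the same images carry at least as much information as one, and a study of 20 patients has little to spare. How much is lost depends on how closely the two readers' AUC differences move together.

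**Working it through.** The plan gives no AUC, AUC difference, standard error or power for the ROC comparison, so there is no figure of its own to reproduce on this point. Section 7 sizes a mean difference (2.1, SD 5.2), not an AUC.

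**Inputs**
- From the documents: two readers for caries (Section 5), ROC by evaluator (Section 8.2), alpha 0.05 (Section 7, taken here as two-sided), 20 patients (Sections 7 and 8.1).
- Assumed: correlation ρ between the two readers' AUC differences, 0.3 to 0.9; equal true effect and equal precision for both readers; approximate normality; 50% power for each reader alone, with 40% and 80% as alternatives.

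**Step 1. Precision of the average.** With equal variances, the variance of the two-reader mean relative to one reader is (1 + ρ)/2, so the SE ratio is √((1 + ρ)/2). For ρ = 0.3 this is √0.65 = 0.806; for ρ = 0.9 it is √0.95 = 0.975.

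**Step 2. Disagreement on significance.** At 50% power each test statistic is centred on the critical value 1.96. Ignoring the negligible far tail, the chance that exactly one reader is significant is 0.5 − arcsin(ρ)/π. For ρ = 0.5 this is 0.5 − 0.5236/3.1416 = 0.333.

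**Step 3. Power of the averaged test.** At 50% power per reader it is Φ(1.96/√((1 + ρ)/2) − 1.96). For ρ = 0.5: Φ(1.96/0.866 − 1.96) = Φ(0.303) = 0.62.

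**Step 4. Type I error if either reader sufficed.** This is one minus the bivariate normal probability that both statistics lie within ±1.96 under no difference.

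| ρ | SE ratio | Disagree, 50% power each | Averaged power | Type I error, either reader |
|---|---|---|---|---|
| 0.3 | 0.81 | 40% | 68% | 9.5% |
| 0.5 | 0.87 | 33% | 62% | 9.1% |
| 0.7 | 0.92 | 25% | 57% | 8.3% |
| 0.9 | 0.97 | 14% | 52% | 7.0% |

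**Step 5. Other power levels.** At 40% power per reader, disagreement runs from 39% (ρ = 0.3) to 14% (ρ = 0.9), and averaged power from 56% to 42%. At 80%, disagreement runs from 27% to 10%, and averaged power from 93% to 82%.

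**Step 6. If both readers were required instead.** P(both) = 0.05 + 0.05 − P(either), so type I error would be 0.10 − 0.095 = 0.5% at ρ = 0.3 and 0.10 − 0.070 = 3.0% at ρ = 0.9. That rule is conservative. At 50% power per reader its power is 0.5 minus half the disagreement rate: about 30% at ρ = 0.3 and 43% at ρ = 0.9.

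**Step 7. If the readers differ in truth.** Suppose one reader has 80% power (mean 1.96 + 0.84 = 2.80), the other has no effect, and ρ = 0.5. The average has mean 1.40 and SE 0.866, so its power is Φ(1.40/0.866 − 1.96) = Φ(−0.34) = 37%. The gain in Step 3 is not guaranteed.

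**The case against.** Testing reader by reader is inferred. Only the curves are said to be per evaluator; the DeLong sentence names the modalities and not the readers. This stands as a limit on the wording. It does not close the gap: if the readings were pooled, the plan does not say how.

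A reader might infer that every accuracy question gets two answers. The documents do not support that. Sensitivity, specificity, McNemar and Wilcoxon are not described as reader-specific. Bone level is a millimetre measurement with no stated disease threshold, so ROC for it is undefined. Furcation has no named reader. The inter-observer analysis implies overlapping readings, but the plan does not say that every image was read twice.

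A reader might also infer that the plan nearly doubles the type I error. It contains no rule that either reader suffices, and requiring both would err in the other direction (Step 6). The inflation is conditional on a rule nobody wrote.

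The correlation and the power are assumptions, and at ρ = 0.9 the gain in precision is small. Averaging is also a trade-off even with fixed readers, because it can hide a reader-by-modality difference (Step 7). Both points stand. They limit the claim about precision, but not the claim that the plan lacks a route from two readers to one result.

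Finally, resampling 20 patients is not exact. Even for a simple normal mean, a percentile-type interval at n = 20 has a type I error of about P(|t| on 19 df > 1.96 × √(19/20)) = 7.1%. This stands, and the remedy needs a small-sample correction.

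**Conclusion.** The point holds in a limited form. For caries, the plan produces reader-specific ROC results and gives no way to reach one conclusion about the modality. The same applies to furcation only if both periodontists score it.

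Given equal true effect and precision in both readers and a correlation of 0.3 to 0.9, averaging would reduce the SE of the AUC difference by 19% to 3%. At 50% power per reader, separate tests would disagree on significance in about 40% to 14% of trials. None of these inputs comes from the documents. The need for a stated route from two readers to one result does not depend on the precision gain being large.

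This is a worthwhile, cheap improvement to the main accuracy comparison. It does not invalidate the data.

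**What to change.** In Section 8.2, for each rated task with two readers, make the main ROC comparison the vertical-minus-horizontal AUC difference averaged over those two readers, treated as fixed. Use each reader's first reading, because Section 8.3 has readings at two time points.

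Obtain the 95% CI and p-value by patient-level resampling that keeps all of a patient's surfaces, both modalities and both readers together. Include a small-sample correction for 20 patients, for example a patient jackknife with t on 19 df. This also deals with several surfaces per patient, which ordinary DeLong ignores; that is a separate reason for the same method.

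Report reader-specific curves and AUCs as supportive, flag any reader-by-modality difference, and state that conclusions apply to these readers. State who rates furcation.

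The cost is SAP wording and modest extra analysis of existing readings. Section 8 already allows MedCalc or equivalent software. The downside is that an average can mask a difference between readers, so the supportive table must be shown. Much of the document is in the past tense, although Section 8 also says that data will be analysed. If the readings have already been analysed, the change must be labelled post hoc.

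### Section 8.2 scores AUC against a partly radiographic reference of unstated source; as written it appears to include the bitewings under test, so the DeLong comparison cannot by itself show which view is more accurate

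*Combined protocol and SAP*

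**What the plan says.** Section 8.2 plots ROC curves per evaluator for each bitewing type, computes AUC against a gold standard described only as a "combined clinical and radiographic diagnosis", and compares the AUCs with DeLong's test. Of sensitivity and specificity it says: "These were calculated for each radiographic method in detecting caries and furcation involvement". No separate reference is named for them.

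Section 5 lists four horizontal and four vertical bitewings per participant and no other imaging. Section 8.1 defines the analysis set as "All radiographs captured for the 20 enrolled participants (160 total bitewing images: 80 vertical, 80 horizontal". Periapical and panoramic images appear only in the titles of cited works. Section 6 describes how the bitewings are scored and measured, but no clinical examination.

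On blinding, section 8.1 says "evaluators were blinded to image type and patient identity", and section 5 says "Observers included two restorative specialists (for caries) and two periodontists (for bone loss), all blinded to group assignments".

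Section 9 expects: "Vertical bitewings will provide better diagnostic accuracy for approximal caries and alveolar bone loss".

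**The concern.** The primary objective is comparative accuracy, and the DeLong test is the analysis that addresses it. That test is interpretable only if the reference does not depend on the images being compared. When a test's own result helps to decide the true status, its errors are counted as correct. If the two views enter the reference unequally, the one with more influence gains AUC and the other loses it, even when they are equally accurate. If they enter equally, both AUCs can be inflated.

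The blinding in section 8.1 does not cure this. It protects the scored readings from knowledge of image type and patient, but does not keep the reference separate from the study images.

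At stake is the section 9 claim that vertical bitewings are diagnostically more accurate.

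**Working it through.** **1. What the plan lets us identify.** 20 participants × 4 images = 80 per view, and 80 + 80 = 160. This reproduces the count in section 8.1, so every image counted there is an index test. The reference has a radiographic part, and no other image is described that could supply it. Incorporation is therefore the natural reading. It is not a stated fact: section 4 recruits people presenting for treatment, who may have had earlier films.

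**2. Size if study bitewings were used.** The plan gives no figure to reproduce, and every input here is assumed.
- Prevalence is 25%. Clinical specificity is 0.95 and sensitivity 0.5 or 0.7.
- Latent score = 1.5 × true status + standard normal error, so the continuous AUC is Φ(1.5/√2) = 0.86. On a five-point rating it is about 0.84 for both views.
- Error correlation is 0 or 0.3 between views, and 0, 0.3 or 0.6 between two readings of one image.
- A radiograph is positive at a rating of 4 or more. When both sets are used, either one positive suffices.
- The reference is positive if clinical or radiographic is positive (OR), or only if both are (AND).
- 400,000 surfaces are simulated per scenario.

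Scored means that the analysed ratings themselves enter the reference. Separate means that a different reading of the same images does.

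| Study images in the reference | OR rule | AND rule |
|---|---|---|
| One view, scored | 0.16 to 0.25 in favour of that view | 0.11 to 0.16 |
| One view, separate | 0.00 to 0.14 | 0.00 to 0.09 |
| Both views, equal thresholds | 0.00 | 0.00 |
| Both, vertical read 0.4 SD more liberally, scored | +0.08 to +0.10 for vertical | about +0.01 or less |
| Both, same shift, separate | 0.00 to +0.05 | about 0.00 |

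The 0.00 with separate readings of one view arises when no image-specific error is shared between the readings. The one-view endpoints move by up to about 0.03 with the placement of the rating cut-points.

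**3. A different model.** Here prevalence is 30% and the reference is the top 30% of summed scores. With a true AUC of 0.76 for both views, clinical plus vertical gives 0.88 for vertical and 0.63 for horizontal, a false gap of 0.25. With a true AUC of 0.85 the figures are 0.91 and 0.71, a gap of 0.20. Clinical plus both views gives no gap but inflates both AUCs, to 0.83 and 0.88 respectively. The pattern is the same.

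**4. What a clinical-only reference costs.** If clinical error is independent of image error given true status, then

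observed AUC = 0.5 + (true AUC − 0.5) × (PPV + NPV − 1).

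- Sensitivity 0.5: PPV = 0.125/0.1625 = 0.769 and NPV = 0.7125/0.8375 = 0.851. The factor is 0.62, and AUC = 0.5 + 0.34 × 0.62 = 0.71.
- Sensitivity 0.7: PPV = 0.175/0.2125 = 0.824 and NPV = 0.7125/0.7875 = 0.905. The factor is 0.73, and AUC = 0.75.
- Sensitivity 0.2: PPV = 0.05/0.0875 = 0.571 and NPV = 0.7125/0.9125 = 0.781. The factor is 0.35, and AUC = 0.62.

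A true difference of 0.10 shrinks by the same factor, to about 0.06, 0.07 and 0.035. Equal views stay equal. If instead 20% of the clinical error variance is shared with horizontal images, equal views show a false gap of 0.08 to 0.10 against vertical. The clinical record must therefore be free of any radiograph, not only the study bitewings.

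**The case against.** The strongest reply is that only an omission is documented. The plan is very brief: it describes no clinical examination either, although section 8.2 relies on clinical findings. Absence of a description is therefore weak evidence that other films were not used. This stands, and it limits the point to what the reference appears to do.

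The figures also depend on a combination rule that the plan does not state. Under AND the one-view gap is smaller, and the effect of unequal thresholds nearly disappears. This stands too, so both rules are shown. The largest gaps require the scored readings themselves to enter the reference. Evaluators blinded to patient identity could not have combined their own scores with that patient's clinical findings. Someone else could have done so later, but no section says so.

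Composite references are common in this field. That is true, but it does not excuse leaving the source, assessor and rule unstated, and the remedy does not forbid a composite.

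A reader might infer more than the documents support:
- That the index tests certainly fed the reference. Existing clinic images cannot be excluded.
- That the bias favours vertical bitewings. Section 1 says they show more root and apico-coronal detail, which makes unequal thresholds plausible, but the direction depends on which images were used and how.
- That using both views always creates a false gap. At equal thresholds it does not.
- That a composite from both views always hides most of a true difference. A true 0.10 shrinks to 0.03 to 0.05 under OR, but only to 0.07 to 0.09 under AND.

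**Conclusion.** The point holds as an undefined reference standard that, on the plan's own description, appears to incorporate the index tests. If any study bitewing contributed, the DeLong comparison cannot by itself support the section 9 claim of better diagnostic accuracy. The same limit applies to sensitivity and specificity, for which no other reference is named.

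The false AUC gap could be nil (both views at equal thresholds, or separate readings sharing no image-specific error) or as large as 0.25 (one view, scored readings, OR rule). That range rests wholly on the assumed inputs, and the documents fix neither its size nor its sign. It would be wrong to read the whole analysis as compromised: the Wilcoxon and McNemar comparisons in section 8.4 set one view against the other without this reference and are unaffected.

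This should be corrected. Confidence is medium, because incorporation is inferred.

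**What to change.** In section 8.2:

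1. State the source of the radiographic component, who made the reference diagnosis, and the rule for combining clinical and radiographic findings.
2. If any study bitewing contributed, report AUC, sensitivity and specificity as agreement with a composite reference, and do not base a claim that one view is more accurate on the DeLong test.
3. If only one view contributed, say so and do not interpret the AUC difference.
4. Where clinical findings were recorded separately and without sight of any radiograph, add the same ROC comparison against the clinical component alone, as a sensitivity analysis for caries and furcation. Bone level is left out because the plan describes no clinical bone measurement.

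Items 1 to 3 cost wording and a weaker claim. Item 4 is one re-run, possible only if such a clinical record exists, which no section shows. Its price is attenuation that depends on the unknown clinical sensitivity: AUCs of about 0.71 to 0.75 at sensitivity 0.5 to 0.7, and lower if sensitivity is lower. A small or null difference there would not show that the views are equally accurate. No new radiographs or re-adjudication are needed.

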A Comparison of Horizontal and Vertical Bitewing Radiographs in Detecting Approximal Caries and Interdental Bone Loss in Posterior Teeth: A Diagnostic Accuracy Randomized Cross-Over Clinical Trial

NCT04341636

February 20, 2020

Principal Investigator:

[name]

Departments of Dental Public Health and Periodontology
King Abdulaziz University, Tufts University, Harvard University

Co-Investigators:

[name], [name]
Faculty of Dentistry, King Abdulaziz University

1. Background and Rationale

Bitewing radiographs are a standard diagnostic tool in dental practice, primarily used to detect approximal caries and evaluate interproximal alveolar bone levels. Traditionally, horizontal bitewings have been widely used for these purposes. However, they have limitations in visualizing vertical bone loss, furcation involvement, and root caries.

Vertical bitewing radiographs, by contrast, provide greater visibility of the apico-coronal dimension and root structures, making them potentially more effective for diagnosing periodontal conditions and deeper carious lesions. This study aims to compare the diagnostic accuracy of vertical versus horizontal bitewing images in detecting caries and bone loss in posterior teeth.

2. Objectives

Primary Objective

- To compare the accuracy of vertical versus horizontal bitewing radiographs in detecting approximal caries and alveolar bone loss.

Secondary Objective

- To evaluate the effectiveness of both imaging modalities in identifying furcation involvement.
- To assess the diagnostic clarity and patient suitability for each radiographic approach.

Material and methods:

3. Study Design

This is a two-arm, randomized crossover clinical trial comparing vertical and horizontal bitewing radiographs. The study was conducted at the Faculty of Dentistry, King Abdulaziz University.

Type of Study: Open-label, randomized crossover clinical trial

Study Setting: Faculty of Dentistry, King Abdulaziz University

Registration: ClinicalTrials.gov (NCT04341636)

Ethical Approval: KAU Ethics Committee (#053-06-17)

4. Participants

Inclusion Criteria:

- Age ≥ 18 years
- Presenting for treatment at KAU dental clinics
- Presence of posterior teeth and canines in each quadrant
- No acute periodontal infection
- Non-smokers
- Full ability to open mouth and tolerate X-ray procedures

Exclusion Criteria:

- Systemic conditions complicating treatment
- Pregnancy or lactation
- Prosthesis obscuring CEJ or caries borders

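### Weighted kappa and ICC depend on the mix and spread of scores as well as on reader error, so a higher coefficient on vertical bitewings need not mean smaller reader error.

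*Combined protocol and SAP*

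**What the plan says.** Section 8.3 uses weighted kappa within observers, "for repeated readings of the same radiographs by the same observer at two time points". Between observers it uses the ICC for bone level and weighted kappa "for caries and furcation rating scores between observers". It then grades kappa in fixed verbal bands. Section 6 names the same two families of coefficient and nothing else. The weighting scheme and the form of the ICC are not stated.

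Section 9 lists this expected outcome: "Vertical bitewings will have superior intra- and inter-observer reliability in detecting pathology". That is a comparison between views, although Section 8.3 does not say that the coefficients will be computed or compared by view.

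Section 1 expects the views to differ in what they display. Of horizontal bitewings it says that "they have limitations in visualizing vertical bone loss, furcation involvement, and root caries", and of vertical bitewings that they "provide greater visibility of the apico-coronal dimension and root structures". Section 9 adds: "Vertical bitewings will show higher sensitivity in detecting furcation involvement".

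The plan contains no within-site SD, limits of agreement or percentage agreement, and it does not restrict reliability to sites readable in both views.

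**The concern.** Kappa compares observed disagreement with the disagreement expected from the readers' marginal distributions. ICC compares between-site variance with total variance. Either can change while the readers' error stays the same, if the two views present a different mix or range of findings. The crossover fixes the patients and their true disease. It does not fix what each image displays or which sites can be measured.

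The Section 9 statement has no planned yardstick other than these coefficients. If the vertical coefficients come out higher, the report could say that observers read vertical images more consistently when the readers' error is the same or larger. The bands in 8.3 add to this, because a shift in the mix of findings can appear as a change of verbal grade.

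**Working it through.** The plan states no reliability figure, prevalence, between-site SD or reader error, so there is nothing of its own to reproduce. Every input below is an assumption chosen to show the mechanism with reader error held fixed.

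**1. Yes/no calls.** Two readers, conditionally independent given what the image shows, each with sensitivity Se = 0.85 and specificity Sp = 0.95. Displayed prevalence is p.

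- Positive call rate: m = p·Se + (1−p)(1−Sp)
- Both positive: a = p·Se² + (1−p)(1−Sp)². Both negative: b = p(1−Se)² + (1−p)Sp²
- Raw agreement: Po = a + b. Chance agreement: Pe = m² + (1−m)²
- Kappa = (Po − Pe)/(1 − Pe). Positive agreement = a/m

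At p = 0.05: m = 0.0425 + 0.0475 = 0.09; Po = 0.0385 + 0.8585 = 0.897; Pe = 0.0081 + 0.8281 = 0.8362; kappa = 0.0608/0.1638 = 0.37.

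| p | Raw agreement | Kappa | Positive agreement |
|---|---|---|---|
| 5% | 89.7% | 0.37 | 0.43 |
| 10% | 88.9% | 0.51 | 0.57 |
| 20% | 87.3% | 0.62 | 0.70 |
| 40% | 84.1% | 0.66 | 0.79 |
| 80% | 77.7% | 0.48 | 0.84 |

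From 5% to 20% the 8.3 label goes from Fair through Moderate to Substantial while raw agreement falls. Kappa peaks near 40% and then declines, so more displayed disease does not always raise it. With Se = Sp = 0.90, raw agreement is 82% at every prevalence, yet kappa is 0.25 at 5%, 0.53 at 20%, 0.64 at 50% and 0.39 at 90%. A small shift does little: in the first model, 10% to 12% moves kappa from 0.51 to 0.54, inside one band.

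**2. Five-point ratings, the scale type used in Section 6.** One fixed error matrix for both readers: correct category with probability 0.8, otherwise one category off. Only the distribution of true grades changes.

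| True grades (%) | Exact agreement | Linear kappa | Quadratic kappa |
|---|---|---|---|
| 90/4/3/2/1 | 68% | 0.46 | 0.70 |
| 60/15/10/8/7 | 67% | 0.74 | 0.89 |

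The effect therefore carries over to weighted kappa. The linear value crosses from Moderate to Substantial.

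**3. Bone level.** ICC = s_b²/(s_b² + s_e²), where s_b is the between-site SD and s_e the reader error SD. With s_e = 0.4 mm:

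- s_b = 1.0 mm: 1/(1 + 0.16) = 0.86
- s_b = 1.5 mm: 2.25/(2.25 + 0.16) = 0.93

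Spread drives this, not the amount of bone loss. Range restriction has the same effect. With a skewed distribution of true levels (mean 3 mm, SD 1.5 mm) and s_e = 0.5 mm, ICC is 0.90 over the full range, 0.82 if sites above 5 mm cannot be read, and 0.75 if sites above 4 mm cannot.

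**The case against.** The strongest reply is that reliability is a legitimate target in its own right. Kappa and ICC describe how well readings separate sites relative to error, and a view that shows real differences more clearly at equal error is more reliable in that sense. Measures of pure error can reward a view on which both readers see nothing. This stands as a reason to keep both coefficients. It does not support reading a higher coefficient as smaller reader error, and the plan does not say which meaning Section 9 intends.

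The reply continues that the mechanism is assumed. Every patient has both views, Section 8.5 expects few missing evaluations, and no prevalence, spread or unreadable share is given. The larger movements above need a fourfold prevalence gap or a 50% wider SD between views of the same teeth, and no specific mechanism is shown for coronal approximal caries. This stands as a limit on size and direction. It does not remove the possibility, because a furcation hidden on the horizontal image is not a missing evaluation: it is rated, as absent.

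Finally, reliability is not an objective in Section 2, an endpoint in 8.2 or a between-view test in 8.4. That is correct and limits the importance of the point.

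A reader might go further and infer that the coefficients are systematically biased towards the vertical view. The documents do not support that. Kappa falls at high prevalence, ICC does not respond to amount as such, and nothing in the plan fixes where the two views lie on those curves.

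**Conclusion.** The point holds in a limited form. With weighted kappa and ICC as the only measures, a higher vertical coefficient cannot by itself support the Section 9 reliability statement, because the same result can arise at unchanged reader error. Confidence intervals or a test on the coefficient difference would address precision but not this ambiguity.

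Under the stated assumptions the movement can be large (kappa 0.37 to 0.62, linear weighted kappa 0.46 to 0.74, ICC 0.86 to 0.93) or slight (kappa 0.51 to 0.54). Which applies here, and in which direction, cannot be determined from the documents. The conclusion rests on two premises: Section 1's expectation that the views display different things, and the reading that Section 9 implies coefficients by view. The AUC, sensitivity and specificity analyses in 8.2 are untouched. This is a worthwhile correction to a secondary conclusion.

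**What to change.** In Section 8.3:

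- **Bone level.** Base the between-view comparison on within-site SD in mm, between readers and between repeat readings where levels were read twice, and on the mean offset between readers. Use only sites measured in both views, and give a patient-clustered interval for the difference between views.
- **Caries and furcation.** Report weighted kappa per view on sites rated in both views, beside the full distribution of ratings and exact agreement. Common sites alone do not equalise what is displayed, so the distribution is needed to interpret kappa. Do not read a kappa difference or a change of verbal band alone as better reliability. Do not use positive agreement as the comparator: in the first example it rises from 0.43 to 0.70 at fixed reader error.
- **Coefficients.** Keep kappa and ICC as within-view descriptions, with the kappa weights and the ICC form stated in advance.

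In Section 9, reword the reliability line to match: smaller reader error in mm for bone level, and a descriptive statement for the rating scales.

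The cost is SAP wording and a few extra lines of analysis, with no new patients or images. Sites readable in only one view drop out of the comparison, so their number should be reported by view.
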